2.5 Activity tracking

The activPAL will be placed on the upper leg with a waterproof adhesive film by a researcher one working day before each activity regime (Friday). The subjects will be asked to wear the activPAL 24 h per day, showering is allowed but swimming is not. The ActivPAL objectively determines the sort and intensity of physical activity (how much time has been spent walking, standing or sitting/lying: Fig. 3) and is already validated in PwMS²⁸. Physical (in)activity can therefore be accurately determined and

adherence with the activity regimes is measured correctly. Participants are asked to note down the exact time spent sleeping and lying, since the ActivPAL is not able to distinguish between sitting and sleeping.

To facilitate adherence with the activity regimes, participants receive a Polar M200. This is an activity tracker which monitors the number of steps, time spent lying, sitting, walking and running per day (Fig. 4). These data can be controlled online by members of the research team to provide feedback by phone when necessary.

[figure not shown]

Figure 3: example of summary ActivPAL data

Figure 4: example of summary Polar data

2.6. Exercise intensity

To ensure that DWA will be the same during the sit less and exercise regime, ActivPAL data of the sit less and sit regime will be used to individualize training sessions during the exercise regime. ActivPAL is able to estimate workload of activities in MET's. One MET is the energy expenditure of an individual in resting condition ($3.5 \text{ mL} \cdot \text{kg}^{-1} \cdot \text{min}^{-1}$). The amount of MET's as provided by the activPAL is based on how many steps are taken, acceleration and amount of hours walking, standing and sitting/lying. The ActivPAL will be taken off during cycling in the exercise regime. The measurement error of the activPAL in estimating this energy expenditure has been reported to be low for sedentary and light-intensity activities but high for moderate- and vigorous-intensity activities²⁹.

It will be calculated how long subjects need to cycle at an intensity of 50-60% W_{max} to match the workload of the training session with the DWA increase of the sit less regime, compared to the sit regime. The workload of cycling at 50-60% of W_{max} will be calculated using the following equation²⁴: $\text{MET} = 0.0545 \cdot \text{Watt} + 1.4561$ ($R^2 = 0.946$), which describes the relationship between MET's and Watts, based on literature included in the compendium of physical activities²⁷ that actually measured energy expenditure over a range of workloads. The DWA in the sit less and sit regime will be measured with the ActivPAL as described above.

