NEPA has already been shown to significantly improve cardiometabolic risk markers in healthy, sedentary subjects²³, type II diabetes patients²⁴ and obese adults²⁵ and it involves lower intensity physical activities that are probably more feasible than MVPA for PwMS. Moreover, with comparable activity workloads, reducing sitting time by NEPA of longer duration decreases insulin levels and fasting lipid levels more than performing one MVPA bout^{23, 24} that is usually described in current activity guidelines¹⁸. So far however, acute MVPA and NEPA effects on cardiometabolic health in this population have never been described. Therefore, the aim of this study is to investigate whether (1) cardiometabolic health (glycaemic control, blood lipids, inflammation markers and blood pressure) of persons with MS improves when sedentary time is reduced and (2) NEPA results in better cardiometabolic health parameters than (a shorter daily bout of) moderate-intensity exercise when workload of both activities is identical in this population.

2. Methods

A flowchart of the study design is provided in Figure 1. The design of the study, the different activity regimes and the continuous activity monitoring are based on previous research in sedentary subjects²³ and type II diabetes patients²⁴. For practical reasons (subjects are aware of their activity regimen), it is not possible to blind the study. The study is an intervention study with a cross-over design. Participants will follow four regimes of 4 days each including a control, a sit less, a sit and an exercise regime. The order of the sit and sit less regimes will be randomized. Each activity regime will be followed by a wash-out period of 10 days during which subjects will continue their normal lifestyle. Fasting glucose, insulin, inflammation parameters, lipids and blood pressure will be determined at the end of each regime (on day 5).

[figure not shown]

Fig. 1: Flowchart study design. The order of the sit less and sit regime will be randomised. Between each activity regime a wash-out period of 10 days takes place. Abbreviations: d: days, v: visit (v-1,-2: screening visits, v1,3,5,7: attachment of ActivPAL – v2,4,6,12: test days + removing of ActivPAL – v8,9,10,11: exercise sessions)

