 - Mental or physical disability
- Based on historical information not able to walk for 3h per day and stand for 4h per day (e.g. intermittent claudication)

There will be two screening visits, organized at least 10 days before start of the study (Saturday of week 1, see table 1). During the first screening visit, a resting electrocardiogram (ECG) will be assessed, which will be evaluated by a trained professional for medical safety of maximal exercise testing (until volitional exhaustion in combination with a respiratory exchange ratio ≥ 1.1 or failure to maintain 45 RPM). This will be done with an incremental exercise test on a bicycle ergometer during the second screening visit, to assess maximal workload capacity (W_{\max}). The W_{\max} is necessary to calculate intensity of training sessions in the exercise regime (see 3.6 exercise intensity). Subsequently, participants will receive a Polar M200 activity tracker and explanation about its use (see 3.5 activity tracking).

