2.4 Regimes

During each activity regime (4 days), participants will be asked to spend 8h sleeping/lying. Subjects will be allowed to sleep \pm 2 hours less or more and replace this sleeping time by sitting (more or less) as long as sleeping time is the same during all regimes. Each activity regime is followed by a wash-out period of 10 days during which subjects can continue their normal lifestyle, but are not allowed to perform more than 60min of MVPA.

Control regime

To provide feedback on how to change activity patterns in order to comply with the subsequent activity regimes, subjects will start with the control regime. This is a baseline measurement of physical activity during which subjects will be instructed not to change activity patterns during these four days and to note all activities they perform.

Sit regime

Here, participants spend 14h of their day sitting, 1h walking and 1h standing. According to the compendium of Ainsworth et al. (2011)²⁷, this corresponds with a daily workload of activities (DWA) of 27 metabolic equivalents (MET's) per day.

Sit less regime

Each day will consist of 3h walking, 4h standing and 9h sitting. These time frames are chosen to result in a comparable DWA increase as the exercise regime compared to the sit regime (+7 MET's)²⁷. The additional 2h of walking and 3h of standing, compared to the sitting regime, will be done in a minimum of four bouts with a time interval of > 1h. The subjects will be instructed to walk on a slow pace. i.e. 2-3 km/h (e.g. walking during shopping and work related walking in an office).

Exercise regime

One hour of sitting in the sit regime will be replaced with 1 training session (1h) on a cycle ergometer in the research center. The remaining hours of each day have to be spent as follows: 13h sitting, 1h walking and 1h standing for daily care. The intensity of the training session (50-60% of W_{max}) results in a DWA of 34.5 MET's according to the compendium of physical activities²⁷. Duration of training sessions will be adapted individually with ActivPAL data of the sit less and sit regime to identically match DWA increase between the sit less and exercise regime, compared to the sitting regime. Details can be found in '3.6 exercise intensity'.

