After an initial resting period of 10min with participants in a supine position in a quiet room with constant temperature (19-21°C), blood pressure (BP) is measured 3 times at 5-min intervals using an electronic sphygmomanometer (Omron®, Omron Healthcare, IL, USA) from the dominant arm and documented as the mean value of the final 2 measurements.

Body weight

Body weight (in underwear) is determined using a digital-balanced weighting scale to the nearest 0.1kg.

4. Statistical analysis

Statistical analyses are performed by IBM SPSS® version 25.0 (IBM SPSS Statistics for Windows, Chicago, IL, USA). Data are expressed as mean \pm SD.

The differences in outcome between regimens are analysed using linear mixed model analyses with activity regimen and period (order of activity regimen) as fixed factors, and an unstructured covariance structure for the four repeated measurements for each person. Shapiro-Wilk test will be used to test normality of the data ($p < 0.05$) and natural log transformations are performed if the outcome is not normally distributed. Likelihood based methods are used for missing values. Numerical variables are presented as mean \pm SD or as medians (first quartile, third quartile) for baseline characteristics (measured during screening) and estimated mean (SEM) for the other values. Regimens are compared pairwise, whereby P-values $\leq 0.05/6$ (Bonferroni correction) are considered statistically significant to account for multiple testing.

The activPAL will be read out and analysed with the activPAL software. The software is able to determine how much time the subjects spent walking, standing and sitting/lying and is also able to estimate energy expenditure (Fig. 1). This makes it possible to objectively determine the proportion of activity/inactivity. We will determine sleeping time based on reported data since the activPAL is not able to distinguish between sitting and sleeping.

5. Data anonymity

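### Cycling METs come from an equation in Watts alone although a MET is defined per kg, so the per-person workload match behind aim 2 is off by body weight, in a direction the documents do not settle

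*Combined protocol and SAP*

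**What the plan says.** Aim 2, at the end of section 1, compares non-exercise activity with moderate exercise "when workload of both activities is identical in this population". Section 2.4 (Exercise regime) makes this a per-person property: "Duration of training sessions will be adapted individually with ActivPAL data of the sit less and sit regime to identically match DWA increase" between the two regimes, relative to sit.

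Section 2.6 gives the mechanics.

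- The sit less and sit workloads are ActivPAL MET estimates.
- The cycling workload comes from MET = 0.0545 × Watt + 1.4561 (R² = 0.946), "which describes the relationship between MET's and Watts, based on literature included in the compendium of physical activities".
- Cycling time at the training load is then solved so that the two increases agree.
- The same section says "One MET is the energy expenditure of an individual in resting condition", with the value 3.5 mL/kg/min.
- The ActivPAL is taken off during cycling.

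Two relevant measurements already exist. The graded test at visit -1 runs "until volitional exhaustion in combination with a respiratory exchange ratio ≥ 1.1" or until cadence fails (section 2.2, Screening). On test days, "Body weight (in underwear) is determined using a digital-balanced weighting scale to the nearest 0.1kg" (section 3, Body weight). Neither enters the sizing of sessions.

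**The concern.** A MET is a rate per kg. The oxygen cost of a given ergometer load, in mL/min, is usually taken to vary little with body mass. Under that premise the same load is worth fewer METs in a heavier person, yet the equation gives everyone at that load the same value.

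The design does not absorb the error.

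- The equation is used only for the exercise regime, so the within-person contrast does not cancel it.
- With the ActivPAL off, no measurement of delivered cycling workload is described.
- The mixed model in section 4 has only regimen and period as fixed factors, so achieved workload never enters the analysis.

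What is at stake is the premise of aim 2. If the workloads differ, a sit less versus exercise difference mixes the type of activity with its amount.

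**Working it through.** **The plan's own totals.** Take lying and sitting as 1 MET (assumed).

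- Sit: 8 + 14 + walking + standing = 27, so walking + standing = 5.
- Sit less: 2 more hours walking, 3 more standing and 5 fewer sitting give +7, so 2 × walking + 3 × standing = 12.
- Solution: walking 3 MET, standing 2 MET. Sit = 8 + 14 + 3 + 2 = 27 and sit less = 8 + 9 + 9 + 8 = 34, as stated.
- Exercise: 8 + 13 + 3 + 2 = 26, so a total of 34.5 puts the nominal cycling hour at 8.5 MET.
- By the equation, 8.5 MET needs (8.5 − 1.4561) / 0.0545 = 129 W.

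The totals reproduce. They are nominal; the individual match rests on the equation.

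**What the slope implies.** In the protocol's units, 0.0545 MET per Watt equals 0.0545 × 3.5 × kg mL O2/min per Watt: 9.5 at 50 kg, 11.4 at 60, 15.3 at 80 and 19.1 at 100. If the true cost per Watt is about the same for everyone, the equation can be right at only one weight for a given wattage. Under that premise the load-dependent METs at 55 kg and 95 kg differ by 95/55 = 1.73-fold.

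**Model for the size (assumptions, not in the documents).** Mass-based MET = I + s × W / (3.5 × kg), with s = 10-12 mL/min per Watt and non-load term I = 1.4561-2.0 MET. Loads of 50 W and 80 W are illustrative.

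**Break-even weight** = s × W / (3.5 × (0.0545 × W + 1.4561 − I)):

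| I (MET) | Load | s = 10 | s = 12 |
|---|---|---|---|
| 1.4561 | any | 52.4 kg | 62.9 kg |
| 2.0 | 80 W | 59.9 kg | 71.9 kg |
| 2.0 | 50 W | 65.5 kg | 78.6 kg |

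At s = 13, I = 2.0 and 50 W it rises to 85.1 kg.

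**Delivered workload at 80 W.** The equation gives 0.0545 × 80 + 1.4561 = 5.82 MET. For +7 MET-h net of 1 MET sitting, time = 7 / 4.816 = 1.453 h (87 min). Delivered = 1.453 × (mass-based MET − 1):

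| Weight | s = 10, I = 1.4561 | s = 12, I = 1.4561 | s = 10, I = 2.0 | s = 12, I = 2.0 |
|---|---|---|---|---|
| 55 kg | 6.70 (4% short) | 7.91 (13% over) | 7.49 (7% over) | 8.70 (24% over) |
| 75 kg | 5.09 (27% short) | 5.98 (15% short) | 5.88 (16% short) | 6.77 (3% short) |
| 95 kg | 4.16 (41% short) | 4.86 (31% short) | 4.95 (29% short) | 5.65 (19% short) |

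At 75 kg and 50 W the range is 26% short to 3% over.

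**Gross or net.** Section 2.6 does not say whether the sitting displaced by cycling is subtracted. At 80 W and +7 MET-h, net accounting gives 87 min and gross accounting 7 / 5.816 = 1.204 h (72 min). Section 2.4 replaces an hour of sitting with cycling, which suggests net.

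**The case against.** A reader might infer that sessions are too short for most adults, and hence that the error tilts aim 2 toward sit less. The documents do not support this. They give no distribution of weight or Wmax and no body weight for the data behind the equation. The low break-even range of 52-63 kg appears only if the non-load term is held at 1.4561 MET for everyone. Relaxing it moves break-even well into ordinary adult weights, and at 55 kg the sign already depends on the inputs. This objection stands in full.

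The 1.73-fold figure does not follow from the MET definition alone. It also needs oxygen cost per Watt to be independent of mass, which is an outside premise. The gross or net convention, left unstated, moves the session by an amount comparable with the error at 75 kg. Both points stand.

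It can also be argued that a better cycling figure would not restore the match, because the sit less side remains a device estimate. Resizing sessions would also change the amount of exercise given, and for heavier participants lengthen sessions well past the nominal hour in section 2.4. These points limit the remedy to reconciling the text and reporting achieved workload. They do not rescue the claim of an identical match.

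Finally, the respiratory exchange criterion implies gas analysis, but no stored VO2-by-load data are described. Availability has to be confirmed. The high R² is no answer: section 2.6 ties the equation to a range of workloads and says nothing about accuracy across body weights.

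**Conclusion.** The concern holds for the match, not for a direction of bias. A per-kg unit and a Watt-only conversion cannot together give an identical workload for each person across a range of body weights. The error enters only the exercise regime and nothing planned would detect it.

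The size rests on assumed inputs: oxygen cost per Watt nearly independent of mass at 10-12 mL/min, a non-load term of 1.46-2.0 MET, and net accounting. On these, break-even is roughly 52-79 kg at 50-80 W (about 85 kg at 13 mL/min per Watt), and the shortfall at 75 kg and 80 W is about 3-27%. Heavier participants than break-even receive less cycling workload than intended and lighter ones more. The net effect on sit less versus exercise depends on the sample's weights and wattages and is unknown.

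**What to change.** In the protocol, reconcile three statements: the per-kg MET definition and the Watt-only equation in section 2.6, and the matching claim in section 2.4. State whether cycling METs are gross or net of the sitting displaced. How sessions are sized is for the investigators; no length or intensity is proposed here.

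In the analysis plan:

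- For every participant, compute delivered cycling MET-h from their own body weight and the visit -1 gas-exchange data where usable: METs = VO2 at the training load / (3.5 × kg), multiplied by the time cycled, on the stated gross or net basis.
- Report the achieved exercise-minus-sit-less workload difference.
- Repeat the sit less versus exercise contrast as a sensitivity analysis, for example restricted to participants whose achieved workloads agree within a margin set in advance.
- If the difference is material, do not word the aim 2 conclusion as a comparison at identical workload.

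The cost is a few lines of text and one derived variable. If the gas data were kept, no new measurement is needed, since weight is taken on every test day. The limits should be stated: VO2 lags load in an incremental test, the sit less side stays an ActivPAL estimate, a restricted subset of 31 people will be imprecise, and exercise is always the last period, so this analysis cannot separate workload from period.

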2.7 Diet

Subjects will be asked not to consume any alcohol during the study and to only consume one serving of alcohol per day during the wash-out period. The use of dietary supplements (e.g. fish oil capsules, polyphenols and vitamins) will be prohibited after screening and during the study. All medication needs to be continued, no changes in the dose or type of medication are allowed during the study and timing of intake will be standardized.

Subjects will be asked to continue their normal diet and to write down in a diary each day what they eat and drink. The diet that is consumed during the first regime needs to be exactly the same during the following regimes. This ensures that energy intake and proportionality of macronutrients will be similar during all four regimes. The meal on the evening before the test day needs to be consumed at similar time points, no food is allowed after this last meal and coffee and tea only up till 20h.

3. Endpoints

On the fifth day of each activity regime the subjects will come in the morning to the laboratory to undergo fasting blood sampling, an oral glucose tolerance test and to measure body weight and blood pressure. Subjects will be asked to use public transportation or car, in order to ensure that subjects are not physically high active on the test day. The subjects need to refrain from smoking, food and drinks except water starting at 20h the day before. Water is allowed until 6h of the test day.

Primary endpoints:

Physical activity

Physical activity and sedentary behaviour will be measured with the ActivPAL3™ activity monitor (PAL Technologies Ltd, Glasgow, UK).

Venous blood samples will be collected to assess glycaemic control and fasting blood parameters:

- Glycaemic control

A standardized two-hour oral glucose tolerance test (OGTT) will be performed to explore effects on insulin sensitivity. The OGTT is chosen as a measure for insulin sensitivity because of its relative simplicity and its acceptable correlation with the gold standard (hyperinsulinemic euglycemic clamp)³⁰. Subjects ingest a solution (250ml) containing 75g dextrose, and venous blood samples are obtained at t=-5, 15, 30, 45, 60, 90 and 120min for assessment of venous glucose and insulin concentration. From glucose and insulin concentrations, homeostatic model assessment for insulin resistance (HOMA-IR) is calculated by: $\text{fasting glucose (mg/dl)} * \text{fasting insulin } (\mu\text{U/ml}) / 405^{31}$ and whole-body insulin sensitivity index (ISI): $10000 / \sqrt{[\text{fasting glucose (mg/dl)} * \text{fasting insulin } (\mu\text{U/ml})] * (\text{mean glucose during OGTT (mg/dl)} * \text{mean insulin during OGTT } (\mu\text{U/ml}))^{30}}$ will be calculated. The area under the curve (AUC) for glucose and insulin for the 2-hour period is calculated using the trapezoidal method³².

- Fasting blood parameters

After antecubital catheter placement, fasting blood samples are obtained for the measurement of glucose, insulin, lipid spectrum parameters (total cholesterol, high density lipoprotein cholesterol (HDL-cho), low density lipoprotein cholesterol (LDL-cho), non HDL cholesterol, triglycerides (TG), apolipoprotein B (apo B), apolipoprotein A1 (apo A1), free fatty acids) and systemic inflammatory markers (C-reactive protein (CRP), interleukin 1 (IL-1) and interleukin 6 (IL-6)).

For blood glucose assessment, blood will be collected in NAF/KO tubes (6ml) and stored in a refrigerator at 4°C for a maximum of 30min. For the assessment of insulin, inflammation parameters and lipid spectrum parameters, blood will be collected in 3 SST tubes (6ml), which will be allowed to clot for 30 min at room temperature. After 30min all tubes will be centrifuged during 12min at 1020 x g at a temperature of 20°C. Afterwards, plasma and serum samples are immediately portioned into aliquots and stored at -80°C until analysis at the end of the trial.

Secondary endpoints:

Blood pressure

After an initial resting period of 10min with participants in a supine position in a quiet room with constant temperature (19-21°C), blood pressure (BP) is measured 3 times at 5-min intervals using an electronic sphygmomanometer (Omron®, Omron Healthcare, IL, USA) from the dominant arm and documented as the mean value of the final 2 measurements.

Body weight

Body weight (in underwear) is determined using a digital-balanced weighting scale to the nearest 0.1kg.

4. Statistical analysis

Statistical analyses are performed by IBM SPSS® version 25.0 (IBM SPSS Statistics for Windows, Chicago, IL, USA). Data are expressed as mean \pm SD.

The differences in outcome between regimens are analysed using linear mixed model analyses with activity regimen and period (order of activity regimen) as fixed factors, and an unstructured covariance structure for the four repeated measurements for each person. Shapiro-Wilk test will be used to test normality of the data ($p < 0.05$) and natural log transformations are performed if the outcome is not normally distributed. Likelihood based methods are used for missing values. Numerical variables are presented as mean \pm SD or as medians (first quartile, third quartile) for baseline characteristics (measured during screening) and estimated mean (SEM) for the other values. Regimens are compared pairwise, whereby P-values $\leq 0.05/6$ (Bonferroni correction) are considered statistically significant to account for multiple testing.

The activPAL will be read out and analysed with the activPAL software. The software is able to determine how much time the subjects spent walking, standing and sitting/lying and is also able to estimate energy expenditure (Fig. 1). This makes it possible to objectively determine the proportion of activity/inactivity. We will determine sleeping time based on reported data since the activPAL is not able to distinguish between sitting and sleeping.

5. Data anonymity

All data will be handled confidentially and coded (RST-subject number 0→31). A subject identification list will be used to link data to the subjects. The key to the code will be safeguarded by an independent investigator that is not involved in the study. All collected data will be stored in Case Report Forms at the Google drive file stream and only members of the research team will have access to the source data. Source data will be stored for 25 years in accordance with GCP standards to re-use them or to validate results. Future research in line with the current study (re-use of the data) will only be conducted with subject's approval on the informed consent form for re-use of the data and approval of the new study by the ethical committee.

Abbreviations:

Apo: apolipoprotein

AUC: area under the curve

BP: blood pressure

CRP: C-reactive protein

DWA: daily workload of activities

ECG: electrocardiogram

EDSS: Expanded disability status scale

HC: healthy controls

HDL chol: high-density lipoprotein cholesterol

HOMA-IR: homeostatic model assessment for insulin resistance

IL-1: interleukin 1

IL-6: interleukin 6

LDL chol: low-density lipoprotein cholesterol

MET: metabolic equivalent of task

MVPA: moderate to vigorous physical activity

NAF/KO tube: sodium fluoride / potassium oxalate tube

NEPA: non-exercise physical activity

OGTT: oral glucose test

PwMS: persons with multiple sclerosis

RPM: rounds per minute

SD: standard deviation

SST: serum separator tube

TG: triglycerides

WBISI: whole-body insulin sensitivity index

W_{max} : maximal workload capacity

References

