2.2 Subjects

Sample size

The study population will involve 31 PwMS. The number of subjects needed for this study has been calculated based on triglyceride level changes in a comparable study by Duvivier and colleagues²⁴ with 3 activity regimes (paired t-test: effect size 0.71, correlation 0.50, 2-sided α of 0.05/6, power 80%, drop-out 10%). Serum triglycerides, which are significantly elevated in PwMS¹⁵, are an important cardiometabolic risk marker²⁶ and improve consistently in 2 comparable studies in sedentary subjects and type II diabetes patients^{23, 24}.

Recruitment

PwMS will be recruited using online and paper advertisements (local physiotherapists, MS-Liga, hospitals). All subjects will be informed in detail and will be asked to provide written informed consent. The study will be approved by the medical ethical committee of Hasselt University and will be performed at Hasselt University (Diepenbeek, Belgium) between February 2019 and September 2020 in accordance with the principles of the Declaration of Helsinki. The present study is registered at clinicaltrials.gov.

Screening

The following subject characteristics will be assessed: age, sex, medications, smoking history and family history of coronary artery disease, type of MS (relapsing remitting, secondary progressive, primary progressive), duration of MS and Expanded disability status scale (EDSS) score.

In order to be eligible to participate in this study, a subject must meet all of the following criteria:

- Signed informed consent
- Men and women ≥ 18 years old
- Clinical diagnosis of MS (McDonald criteria)
- EDSS ≤ 5
- Daily internet access

A potential subject who meets any of the following criteria will be excluded from participation in this study:

- Reported participation in another biomedical trial which may have an effect on blood parameters one month before the pre-study examination or during the study
- Blood donation in the past three months
- Pregnancy or intention of becoming pregnant
- Reported dietary habits: medically prescribed diet, slimming diet
- Reported weight loss ($>2\text{kg}$) in the last three months prior to the screening
- Alcohol use > 20 units per week (during the last 3 months)
- Experimental drug use (during the last 3 months)
- Medication changes (during the last month)
- Medical conditions which make participation in the study not responsible:
 - Heart failure NYHA 3 or higher
 - Angina pectoris or signs of cardiac ischemia during exercise testing

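### Seventeen blood outcomes and activPAL activity are all primary with no lead or testing order; the 0.05/6 threshold covers only the six regimen pairs within one outcome

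*Combined protocol and SAP*

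**What the plan says.** **Endpoints (section 3).** The first item under Primary endpoints is physical activity and sedentary behaviour measured by activPAL. The second is introduced by "Venous blood samples will be collected to assess glycaemic control and fasting blood parameters". The glycaemic part rests on an oral glucose tolerance test that "will be performed to explore effects on insulin sensitivity" and yields four derived measures. For the rest, "fasting blood samples are obtained for the measurement of glucose, insulin, lipid spectrum parameters", followed by inflammatory markers. Only blood pressure and body weight are secondary.

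**Analysis (section 4).** Each outcome is analysed by "linear mixed model analyses with activity regimen and period (order of activity regimen) as fixed factors". Regimens are compared in pairs, and P-values at or below 0.05/6 ("Bonferroni correction) are considered statistically significant to account for multiple testing"). No other multiplicity rule appears.

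**Sample size (section 2.2).** The number of participants "has been calculated based on triglyceride level changes in a comparable study", using a paired t-test at two-sided 0.05/6. The same paragraph argues for triglycerides as a risk marker, but neither it nor section 3 calls them the lead endpoint.

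**Aims (end of section 1).** There are two: whether cardiometabolic health improves when sedentary time falls, and whether light activity does better than exercise of equal workload. Neither says which measure decides the answer.

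**The concern.** A divisor of 6 offered as the correction for multiple testing looks complete until one asks what the 6 counts. It counts regimen pairs. The outcomes form a second dimension, 17 wide for blood alone, and the plan leaves it unrestricted. Nothing in the text stops a significant pair in any one of those outcomes from being reported as the trial's primary result, and the chance that such a result is false has no stated limit.

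Two consequences follow. A reader of the final report cannot tell whether a highlighted outcome was chosen before or after the data were seen. And the stated power belongs to an outcome that the endpoint list treats like the other 16. ActivPAL activity adds to the ambiguity: it is primary too, with several measures (walking, standing, sitting or lying, estimated energy expenditure). Yet the regimens themselves prescribe it, so a difference there shows adherence rather than benefit.

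**Working it through.** **1. Count the outcomes (section 3).**
- Glycaemic control: HOMA-IR, ISI, glucose AUC, insulin AUC = 4
- Fasting glucose and insulin = 2
- Lipids: total, HDL, LDL and non-HDL cholesterol, triglycerides, apo B, apo A1, free fatty acids = 8
- Inflammation: CRP, IL-1, IL-6 = 3

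4 + 2 + 8 + 3 = 17 blood outcomes. ActivPAL measures are not counted.

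**2. What the 6 covers.** Four regimens give 4 × 3 / 2 = 6 pairs, so the Bonferroni bound within one outcome is 6 × 0.05/6 = 0.05. Across outcomes there are 17 × 6 = 102 tests. The expected number of false positives under the global null is 102 × 0.05/6 = 0.85.

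**3. Reproduce the sample size.** Inputs from section 2.2: effect size 0.71, correlation 0.50, two-sided α = 0.05/6 = 0.00833, power 80%, drop-out 10%. With correlation 0.5 the standardised paired difference is 0.71/√(2 × (1 − 0.5)) = 0.71. Exact noncentral-t power is 78.9% at n = 27 and 80.9% at n = 28. Then 28 × 1.1 = 30.8, giving 31, as stated (28/0.9 = 31.1 would round up to 32). The figure holds for one outcome at 0.05/6.

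**4. Chance of at least one false primary blood result.** Simulation with all nulls true, 28 completers, four regimens, 17 equally correlated outcomes and paired t-tests at two-sided 0.05/6. The between-outcome correlation is an assumption. The aims are read as two contrasts: sit less vs sit, and sit less vs exercise. Ranges show the spread over repeated runs.

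| Tests counted | Corr. 0 | Corr. 0.5 | Corr. 0.8 | One outcome only |
|---|---|---|---|---|
| Two aim contrasts, either direction | 23–24% | 16–18% | 9–10% | at most 2 × 0.00833 = 1.7% |
| Two aim contrasts, favourable only | about 12% | about 9% | about 5% | at most 0.8% |
| All 102 tests, either direction | 51–53% | 37–39% | 21–23% | about 4% |

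Several outcomes are linked by formula: HOMA-IR and ISI use fasting glucose and insulin, and non-HDL is total minus HDL cholesterol. Building those links in, with assumed within-person SDs, lowers the last row only slightly, to 48%, 35% and 20%. The favourable-only row becomes 11%, 8% and 4%.

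**5. Compare remedies.** Bonferroni over all 102 tests means α = 0.05/102 = 0.00049. Power at 28 completers falls from 80.9% to 44.2%, and 80% would need 44 completers (44/0.9 = 48.9, so 49 enrolled). One lead outcome with six pairs at 0.05/6 keeps the bound at 5% and the sample at 31.

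**The case against.** The best defence is that the text signals its intent. The multiplicity sentence opens by referring to pairwise regimen comparisons, so its scope is visible and it does not claim control across outcomes. Triglycerides are singled out for sizing and justified at length, and the glucose tolerance test is described as exploratory. In a small, unblinded crossover with four-day regimens, reporting each outcome at its own error rate is a defensible convention, provided nobody claims success on whichever outcome happens to be significant. The plan makes no such claim.

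Much of this stands as context, but it does not set a priority. The glucose tolerance measures are still listed as primary, triglycerides are one item in a lipid list, and no text rules out a primary claim from any single outcome.

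Three stronger readings should be resisted.
- A reader might take 51% (or 58% if 17 outcomes are treated as independent at 0.05 each) as the trial's error rate. Those figures need zero correlation and include control-regimen pairs outside the aims; the measures are partly linked by formula. The aim-based rows are the relevant ones, and at high correlation with only favourable results counted the figure is about 5%.
- A reader might infer that the sample size is wrong. It reproduces from its own inputs.
- A reader might add that the period term in the mixed model makes some regimen pairs impossible to estimate, since control is always first and exercise always last. That depends on what period means. It is a separate question, and naming a lead endpoint does not resolve it.

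**Conclusion.** The point holds. The plan names activPAL activity and 17 blood outcomes as primary, with no lead and no order, and its one multiplicity rule controls error within an outcome only. On the two aim contrasts, the chance of at least one false primary blood result is roughly 9% to 24%, depending on a between-outcome correlation that the documents do not give. Counting favourable results only, it is roughly 5% to 12%. The comparable bounds for a single outcome are 1.7% and 0.8%.

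These figures assume 28 completers, all nulls true, paired t-tests in place of the mixed model, and my reading of which contrasts the aims imply. The gap itself rests on none of these. It is a gap in endpoint designation: it does not undermine the design or the sample size, and it can be closed without new data.

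**What to change.** Amend section 3, with a matching sentence in section 4:
- Name fasting triglycerides as the single primary endpoint, keeping 0.05/6 and N = 31. Another lead is possible, but triglycerides are the only outcome that the documents size the trial for.
- Reclassify activPAL activity as an adherence or intervention check. Section 2.5 already uses it for that. Without this step triglycerides would not be the only primary endpoint.
- Make the other 16 blood outcomes secondary, either labelled supportive or controlled by Holm or false discovery rate.
- Optionally, test one named glycaemic measure second, within a regimen pair, only when triglycerides are significant for that pair. Error per pair stays at or below 0.05/6, so the total stays at or below 6 × 0.05/6 = 5%. Its power is unknown, because the documents give no effect size for it.

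**Timing.** Section 3 says "plasma and serum samples are immediately portioned into aliquots and stored at -80°C until analysis at the end of the trial", so the amendment should precede the assays. Section 2.2 places the study "between February 2019 and September 2020", so that point may have passed. If the samples have already been analysed, report triglycerides as the lead outcome because the trial was sized on them, and label the rest supportive.

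**Cost.** A protocol amendment, and an update to the registration if it lists the same endpoints (its entry is not among the documents). Participants, visits and assays do not change. The real price is that the other outcomes, including glycaemic control, lose the standing to support a primary claim.
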